2.2 Drug Information

Mechanism of Action

Naltrexone hydrochloride is a competitive antagonist at mu and delta opioid receptors. As such, it blocks the binding of beta-endorphin to the mu opioid receptor. Although naltrexone has been shown to have variable effects on beta-endorphin levels¹⁹⁻²¹, endorphin levels do not predict opioid activity in the presence of a mu opioid receptor antagonist like naltrexone.

Clinical Studies

In human studies, naltrexone has been effective in decreasing both use and cravings in patients with alcohol and opioid dependence^{22,23} Naltrexone (in both oral and long-acting injectable IM formulations) is currently FDA approved for the treatment of alcohol and opioid dependence. Off-label studies have shown efficacy of naltrexone (in combination with bupropion) in causing significant weight loss in patients with uncomplicated obesity²⁴. The agent has also been studied off-label for treatment of binge eating disorder and self-injurious behavior. The placebo-controlled studies that demonstrated the efficacy of naltrexone as an adjunctive treatment of alcoholism (in patients > 18 years of age) used a dose regimen of 50 mg po daily for up to 12 weeks; doses effective for obesity were somewhat lower (16-32mg). Clinically, the standard, widely-utilized, dose, attained in the vast majority of patients with alcohol and opioid

dependence, is 50mg daily. Furthermore, prior research suggests that women achieve higher serum levels of naltrexone than men, and that women are significantly less adherent to 100mg doses (due to decreased tolerability) than to placebo or 25-50mg doses²⁵.

The durations of most placebo-controlled trials of naltrexone for alcohol and opioid dependence have ranged from 12-52 weeks, although shorter positive trials (3-12 weeks) exist in the literature. Clinically, for treatment of alcohol and opioid dependence, an initial 4-month course of naltrexone is recommended, and the medication can be continued indefinitely in the setting of good response.²⁶ The present study differs in that the target population will receive naltrexone for radiotherapy-emergent fatigue, which has been shown in prior studies to improve spontaneously after the conclusion of radiation treatment, returning to pre-treatment levels in the majority of patients by three months after radiotherapy.^{13,15} Therefore, a 5-week trial duration will be utilized in order to minimize the possibility of missing the appropriate time period in which to demonstrate treatment effect as opposed to spontaneous recovery. Further supporting the 5-week trial duration is the observation that patients often demonstrate therapeutic benefit from naltrexone within the first few days or weeks of treatment.²⁷

Pharmacokinetics

Naltrexone has a volume of distribution of 1350 L, and is 21% protein bound. It is metabolized hepatically via dihydrodiol dehydrogenase and conjugation to its principal metabolite, 6-beta-naltrexol. It is 53-75% renally excreted, mostly as metabolites, less than 2% unchanged. The elimination half-life of 6-beta-naltrexone is 5-10 days.

Despite its hepatic metabolism, naltrexone does not interact with the cytochrome P450 enzyme system.

2.3 Rationale

Radiation Therapy

The majority of cancer patients receiving radiation therapy are treated with fractionated external beam radiation, in which a daily dose of radiation from an external source targets a tumor within the body. A significant portion of patients receiving external beam radiation experience fatigue three to four weeks into a typical five- to eight-week radiation course, regardless of the location of the tumor or the radiation field. This fatigue usually lasts for approximately three weeks after treatment and either resolves spontaneously, or can persist for weeks to months.

Interestingly, patients receiving radiation that targets only superficial structures (i.e. breast cancer patients) can become equally as fatigued as patients receiving radiation to deeper structures, and fatigue is more highly correlated with skin dose and field size than with depth of radiation^{28,29}. In fact, the one commonality among radiation therapy regimens that cause fatigue is that there is a significant skin dose. This led us to hypothesize that factors produced in the skin in response to radiation may play a role in radiation-induced fatigue.

DNA damage resulting from radiation exposure causes upregulation of expression of p53 dependent genes in skin cells. One recently-identified p53-dependent gene upregulated in keratinocytes in response to radiation exposure encodes a long-lived endogenous opioid called β -

endorphin³⁰. β -endorphin induction following radiation exposure was observed during studies elucidating the pathway through which ultraviolet radiation stimulates skin pigmentation (tanning). In the pigmentation response following ultraviolet radiation exposure, there is a p53-induced expression of pro-opiomelanocortin (POMC) in keratinocytes. POMC is cleaved into various biologically-functional peptides. One of these peptides, Melanocyte Stimulating Hormone (MSH), is important in the tanning response, acting in a paracrine fashion to stimulate melanocytes to produce pigment. Another peptide derived from POMC production and cleavage following multiple types of DNA damage is the endogenous opioid β -endorphin. Opioid drugs (such as morphine) often cause fatigue and lethargy when they are used to treat pain. [name] data in mice show that plasma β -endorphin levels are elevated significantly by 3 weeks into a 6-week regimen of daily tail radiation that models radiation therapy in cancer patients receiving radiation to superficial structures. In contrast to humans, mice do not exhibit fatigue in response to exogenous administration of opiate drugs³¹. However, quantitative behavioral studies indicated significant changes in phenotypes associated with morphine administration, including mechanical and thermal nociception, in tail-irradiated mice that did not occur in non-irradiated mock-treated counterparts. Furthermore, these changes were reversed upon administration of the opioid antagonist naloxone. In these tail-irradiated mice, β -endorphin plasma levels diminish over the 4 weeks following the end of the radiation regimen.

Chemotherapy

Patients receiving chemotherapy typically become debilitatingly fatigued, even more predictably than radiation therapy patients. As mentioned above, the increased production of β -endorphin following radiation exposure-induced DNA damage is a p53-dependent process. Many common chemotherapeutics are DNA damaging agents that induce p53, and therefore p53-dependent genes, to cause apoptosis of cancer cells³². As transcription of the gene encoding β -endorphin is responsive to p53, it is thus plausible that the fatigue caused in patients receiving chemotherapy is the result of increased β -endorphin production following chemotherapy-induced p53 up-regulation in target cells. A treatment that blocked the effects of β -endorphin might then also reduce any residual fatigue from chemotherapy.

2.4 Correlative Studies Background

At the blood draw obtained for eligibility determination immediately prior to randomization, whole blood samples will be banked for analysis of OPRM1 (mu opioid receptor) genetic variants, specifically the Asn40Asp missense variant which has a frequency of 0.10-0.15 in Caucasians, 0.21 in Ashkenazi Jews, 0.25-0.45 in East Asians, and 0.14 in Hispanics.³³ The Asn40Asp variant has been shown to bind beta-endorphin approximately three times more tightly than the most common allelic form of the receptor,³⁴ and it has predicted good clinical response to naltrexone in alcohol and opioid dependence.^{33,35,36}

Banked specimens will also be available for future exploratory examination of pro-inflammatory biomarkers such as expression-regulating polymorphisms in pro-inflammatory cytokine genes, which in recent studies have correlated with increased fatigue severity, depressive symptoms and memory complaints.³⁷

3. PARTICIPANT SELECTION

3.1 Eligibility Criteria for Monitoring Phase

- 3.1.1 Age \geq 18
- 3.1.2 Diagnosis of: invasive breast cancer (stage I-III), ductal carcinoma in situ, lobular carcinoma in situ, lobular carcinoma
- 3.1.3 Plan to receive radiation therapy, or within 3 days of starting radiation therapy

3.2 Exclusion Criteria for Monitoring Phase

- 3.2.1 Suicidal ideation, as determined via PHQ-9
- 3.2.2 Non-English speaking

3.3 Eligibility Criteria for Randomization Phase

- 3.3.1 Participants may have had prior breast surgery and/or chemotherapy.
- 3.3.2 Age \geq 18 years.

Because no dosing or adverse event data are currently available on the use of naltrexone in cancer patients <18 years of age, children are excluded from this study, but will be eligible for future pediatric trials.

- 3.3.3 Participants must have acceptable pre-treatment laboratory values as defined below:

- total bilirubin within normal institutional limits
 - AST(SGOT)/ALT(SGPT) $\leq 2.5 \times$ institutional upper limit of normal
 - creatinine within normal institutional limits
- OR
- creatinine clearance ≥ 60 mL/min/1.73 m² for patients with creatinine levels above institutional normal.
 - TSH <10 mIU/L

- 3.3.4 If child-bearing potential, willingness to use adequate contraception (hormonal or barrier method of birth control; abstinence) prior to study entry and for the duration of study participation. Should a woman become pregnant or suspect she is pregnant while she or her partner is participating in this study, she should inform her treating physician immediately.

- 3.3.5 Ability to understand and the willingness to sign a written informed consent document

- 3.3.6 Receiving radiation therapy of any type at DFCI, BWH, MGH, or affiliated network sites (including but not limited to partial breast irradiation, two-field, three-field, and four-field plans)
- 3.3.7 FACIT-F subscale score ≥ 10 pre-radiation therapy and decrease in FACIT-F of 10 points or more as compared to prior FACIT

3.4 Exclusion Criteria

- 3.4.1 Participants with major depressive disorder and/or suicidal ideation as determined by PHQ-9.
- 3.4.2 Participants who are receiving any other investigational agents that might interact with study medication or influence the measurement of study outcomes.
- 3.4.3 Participants with known metastatic disease should be excluded from this clinical trial because of their poor prognosis and because they often develop progressive neurologic dysfunction that would confound the evaluation of neurologic and other adverse events.
- 3.4.4 History of allergic reactions attributed to compounds of similar chemical or biologic composition to naltrexone.
- 3.4.5 Participants who have used opioid-containing medications (including cough/cold medications containing codeine and/or antidiarrheals containing loperamide) in the past 2 weeks, or who are expected to require opioid-containing medications within the duration of the treatment period.
- 3.4.6 Uncontrolled intercurrent illness including, but not limited to, ongoing or active infection, symptomatic congestive heart failure, unstable angina pectoris, cardiac arrhythmia, or psychiatric illness/social situations that would limit compliance with study requirements.
- 3.4.7 Pregnant women are excluded from this study because naltrexone is category C agent with the potential for teratogenic or abortifacient effects. Because there is an unknown but potential risk for adverse events in nursing infants secondary to treatment of the mother with naltrexone, breastfeeding should be discontinued if the mother is treated with naltrexone.
- 3.2.8 Participants using other contraindicated medications (thioridazine, yohimbine)

3.5 Inclusion of Women and Minorities

Women of all races and ethnic groups are eligible for this trial.

4. RECRUITMENT AND REGISTRATION PROCEDURES

4.1 Patient Recruitment

The study team will review radiation oncologist's schedules and Epic records for basic information to identify potential patients. With the radiation oncologist's permission, a trained individual will approach the patient to discuss this study. If a patient decides to participate in this study, written informed consent will be obtained.

4.2 General Guidelines for DF/HCC and DF/PCC Institutions

Institutions will register eligible participants with the DF/HCC Quality Assurance Office for Clinical Trials (QACT) central registration system. There will be a two-part registration: the 1st part for the monitoring phase of the study and the 2nd part for the intervention phase. The relevant part of the registration must be completed prior to the initiation of fatigue monitoring (1st part) and therapy (2nd part). Any participant not registered to the protocol before treatment begins will be considered ineligible and registration will be denied.

An investigator will confirm eligibility criteria and a member of the study team will complete the QACT protocol-specific eligibility checklist. The CRC will be consenting participants to monitoring phase only. Intervention phase consent will be done by an MD who is listed as a co-investigator.

Following registration, participants may begin protocol treatment. Issues that would cause treatment delays should be discussed with the Overall Principal Investigator (PI). If a participant does not receive protocol therapy following registration, the participant's registration on the study may be canceled. Notify the QACT Registrar of registration cancellations as soon as possible.

4.3 Registration Process for DF/HCC and DF/PCC Institutions

The QACT registration staff is accessible on Monday through Friday, from 8:00 AM to 5:00 PM Eastern Standard Time. In emergency situations when a participant must begin treatment during off-hours or holidays, call the QACT registration line at [contact] and follow the instructions for registering participants after hours.

The registration procedures are as follows:

- Obtain written informed consent from the participant prior to the performance of any protocol specific procedures or assessments.
- Complete the QACT protocol-specific eligibility checklist using the eligibility assessment documented in the participant's medical record and/or research chart. **To be eligible for registration to the protocol, the participant must meet all inclusion and exclusion criterion as described in the protocol and reflected on the eligibility checklist.**

Reminder: Confirm eligibility for ancillary studies at the same time as eligibility for the treatment protocol. Registration to both treatment and ancillary protocols will not be completed if eligibility requirements are not met for all studies.

- Fax the eligibility checklist(s) and all pages of the consent form(s) to the QACT at [contact]. For Phase I protocols, attach participant dose level assignment confirmation from the sponsor.
- The QACT Registrar will (a) review the eligibility checklist, (b) register the participant on the protocol, and (c) randomize the participant when applicable. The randomization will be a block randomization at each site (DFCI/BWH vs MGH).
- An email confirmation of the registration and/or randomization will be sent to the Overall PI, study coordinator(s) from the Lead Site, treating investigator and registering person immediately following the registration and/or randomization.

[figure not shown]
5. TREATMENT PLAN

5.1 Treatment Regimen

Patients consented to the intervention phase will be randomized to naltrexone (25mg for 1 week, followed by 50mg for 4 weeks) or matching placebo. All participants will be instructed to take the double-blinded medications in the morning with food. The medication should be swallowed whole. If the patient misses or vomits a dose, they can be re-dosed within an 8-hour time frame.

The patient will be requested to maintain a medication diary of each dose of medication. The medication diary will be returned to clinic staff at the end of the study.

Study Plan: Randomization Phase

¹Functional Assessment of Chronic Illness Therapy-Fatigue Subscale

5.2 Pre-Treatment Criteria

No evidence of hepatic or renal impairment and serum HCG negative, as described in the eligibility criteria above

5.3 Agent Administration

All participants will be instructed to swallow the double-blinded medications in the morning with food.

Monitoring and Intervention Phases: Visit Breakdown – Refer to study calendar in section 9.

Monitoring Phase (duration: 1-10 weeks):

- Visit 1: Collection of baseline data.
 - a. Patient demographic information and clinical characteristics will be collected by self-administered surveys.

- b. Completion of self-reported fatigue, anxiety, depression, sleep and quality of life questionnaires.
- Visits 2-10 (in person or by phone): Monitoring procedures including completion of self-reported fatigue and other quality of life questionnaires

The occasional mis-timed (or missed) FACIT does not automatically constitute a protocol violation. However, in order to remain in compliance with the protocol, a minimum of 4 FACITs is needed for partial breast irradiation patients, 5 FACITs for hypofractionation patients, and 7 FACITs for standard (6 week) fractionation patients. The monitoring phase terminates either at entrance into the intervention phase of the study, or at 4 weeks after the conclusion of radiation therapy, whichever comes first.

Intervention Phase (duration 5 weeks):

- Visit 1a:
 - a. consent for trial;
 - b. review of concomitant medications;
 - c. complete baseline fatigue questionnaire (unless completed within past week)—may be completed at Visit 1b;
 - d. complete anxiety, depression, sleep and quality of life questionnaires (unless completed within past week)—may be completed at Visit 1b;
 - e. urine HCG only in women with reproductive potential; blood draw to evaluate LFTs, Hct, BUN/Cr unless results are available within the previous month;
 - f. specimens will be banked for future analysis of fatigue-related genetic polymorphisms and inflammatory biomarkers (participants can opt out of specimen banking)
- Visit 1b: laboratory study results reviewed to confirm eligibility; receive medication bottles and medication diary; receive patient education sheet on contraindicated medications and safety card (see Appendix A); Visit 2 (one week after starting study drug vs. placebo): fatigue/response and adverse event assessment for dose escalation, review of concomitant medications, fatigue assessment
- Visit 3 (five weeks after initiating study drug vs placebo): complete follow-up fatigue, anxiety, depression, sleep and quality of life questionnaires; review of concomitant medications; return medication bottles and diaries. Blood draw for LFTs.

5.4 General Concomitant Medication and Supportive Care Guidelines

For nausea, the suggested approach based on clinical guidance is for the patient to take naltrexone with a tablespoon of simethicone (e.g., Gas-X® and Mylicon®) or bismuth subsalicylate (e.g., Pepto-Bismol).

Drug Interactions with Naltrexone:

The following medications are contraindicated because their effect may be blocked:

- Cough/cold medications: if medication contains an opioid (e.g. codeine)
- Antidiarrheal medications: if medication contains an opioid (e.g. loperamide)

Opioid analgesics: Contraindicated because greater amount of opiate analgesia may be required than usual which may result in deeper and more prolonged respiratory depression than if the patient were not taking naltrexone

Thioridazine: May result in lethargy and somnolence

Yohimbine: May result in anxiety and increased pulse and blood pressure

Nonsteroidal anti-inflammatory drugs (NSAIDs): At doses above that used in this study, may result in liver enzyme elevations (i.e., AST and ALT) in combination with regular use of very high doses of naltrexone (200–250 mg/day).³⁸ This effect has only been observed above the recommended therapeutic dose range of naltrexone (i.e., >50–100 mg); therefore these medications are not considered to be contraindicated.

5.5 Duration of Therapy

Duration of therapy will be five weeks. In the absence of adverse event(s), treatment will continue for the entire five weeks unless one of the following criteria applies:

- Initiation of opioid-containing medications
- Intercurrent illness that prevents further administration of treatment
- Unacceptable adverse event(s)
- Participant demonstrates an inability or unwillingness to comply with the oral medication regimen and/or documentation requirements
- Participant decides to withdraw from the study
- General or specific changes in the participant's condition render the participant unacceptable for further treatment in the judgment of the treating investigator

5.6 Duration of Follow Up

Participants in the monitoring phase of the study will be followed for a maximum of 10 weeks, ending 4 weeks after cessation of radiotherapy or until they consent (if eligible) to participate in the intervention phase of the study. Those in the intervention phase will be followed until 4 weeks post-treatment. Participants removed from study for unacceptable adverse event(s) will be followed until the end of the study and beyond, until resolution or stabilization of the adverse event has occurred.

5.7 Criteria for Removal from Study

1. Initiation of opioid therapy, or newly expected need for opioid therapy while on study drug

2. Emergence of suicidal ideation
3. Moderate or severe hepatic impairment (AST and ALT > 3x ULN; Bilirubin > 1.5 ULN)
4. Moderate or severe renal impairment (Creatinine > 1.5x ULN)
5. Clinically significant respiratory or cardiac disease
6. Significant deviation from study protocol
7. Need to hold drug for more than 3 days, for any reason

Participants will be removed from the study when any of the criteria listed in Section 5.7 applies. The reason for study removal and the date the participant was removed must be documented in the case report form (CRF). Alternative care options will be discussed with the participant.

A QACT Treatment Ended/Off Study Form should be filled out when a participant completes study treatment and again when the participant comes off study. This form can be found on the QACT website or obtained from the QACT registration staff.

[figure not shown]
In the event of unusual or life-threatening complications, investigators must notify the Overall PI, [name], at [contact], [name] or via email ([contact]) within 24 hours of discovery.

Psychiatric emergencies: Suicidal ideation is a rare (<=1%) adverse event associated with naltrexone use in individuals receiving IM naltrexone for alcohol and opioid dependence but it was not observed in those treated with naltrexone orally or in those receiving it for other indications (i.e., obesity, smoking cessation, binge eating disorder). Suicidal ideation will be assessed during the trial each time the PHQ-9 depression self-report questionnaire is completed. The CRC will be scoring the PHQ9 and if the score is greater than or equal to 10, the CRC will notify the participant’s Radiation Oncologist as well as the study’s psychiatrist so that they can discuss with the participant the options for clinical follow-up and further care. Suicidal ideation that is indicated on the PHQ-9 or spontaneously reported will constitute a serious adverse event. This evaluation will be conducted by one of the study clinicians with psychiatric expertise and/or by mental health staff in the MGH or BWH emergency rooms, if appropriate. These participants will be followed by study psychiatrists until a local mental health clinician is available for ongoing treatment. Study medication will be discontinued in any participant who develops suicidal ideation. The following established algorithm will be employed:

Specific Algorithms for Addressing Participant Reports of Suicidal Ideation

Algorithm based on response to PHQ-9:				Algorithm based on participant volunteering possible suicidal ideation	
ITEM 13.9: Over the last 2 weeks, how often have you been bothered by				Ask: Have you had thoughts of actually hurting yourself?	
.... Thoughts that you would be better off dead or of hurting yourself in some way?					
If participant responds (shaded areas)				If participant responds (shaded area)	
Not at all	Several days	More than half the days	Nearly every day	NO	YES
0	1	2	3		

 
Ask: Have you had thoughts of actually hurting yourself? If participant responds (shaded area) NO YES
 
Ask three screening questions about plan, probability and preventing factors:
	
Shaded response requires one of the following to be done the same day:
 
 • Refer participant to study psychiatrist • Send participant to an emergency room, or • Send participant to another mental health professional

Plan: 1. Have you thought about how you might actually hurt yourself? NO YES [ask HOW?]
	

Probability: 2. There's a big difference between having a thought and acting on a thought. How likely do you think it is that you will act on these thoughts about hurting yourself or ending your life sometime over the next month?
 
Not at all likely Somewhat likely Very likely
	

Preventing factors: 3. Is there anything that would prevent or keep you from harming yourself? NO YES [ask WHAT?]
	

Any shaded responses to the three screening questions requires one of the following to be done the same day:
 
 • Refer participant to study psychiatrist • Send participant to an emergency room, or • Send participant to another mental health professional 	

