Intervention phase: Radiation oncologists will consent patients who develop treatment-emergent fatigue developing during or within one month after completion of radiation therapy and who are interested in participating in the intervention phase of the study. After informed consent is obtained and final eligibility determination is complete, participants will have 5 study visits: one at study entry to initiate treatment (week 0), one to rule out any contraindication to the scheduled dose escalation (week 1), one at the conclusion of medication treatment for treatment outcome assessment and safety monitoring (week 5), and the last at four weeks after discontinuation of study drug vs. placebo (week 9). All intervention visits have a window of ± 7 days.

Study treatment: The treatment schedule includes a daily dose of double-blinded naltrexone vs. placebo for 5 weeks. Treatment will be initiated at 25 mg/day (or equivalent placebo) during the first week to improve tolerability. The dose will be escalated to 50 mg/day (or equivalent placebo) after one week barring significant early improvement in fatigue or adverse events precluding dose escalation, and participants will continue to take 50 mg/day (or 25 mg/day if dose is not escalated) for 4 weeks to complete a 5-week treatment period.

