5.8 DOSING DELAYS/DOSE MODIFICATIONS

Study drug will be increased to 50mg after 1 week of therapy unless fatigue has improved substantially on the lower dose or there are contraindications to this planned dose increase (including, but not limited to, adverse events grade II or higher that are thought to be related to study drug), as judged by the research nurse and study psychiatrist.

Some patients may tolerate the 25mg dose but develop toxicity after the dose is increased to 50mg. Hence, drug dose can be decreased from 50mg to 25mg in the setting of new-onset adverse events grade II or higher by CTCAE judged to be definitely or probably related to study drug.

Study drug (either at the 25mg or 50mg dose) can also be held for up to three days and then

restarted in setting of adverse events grade II or higher by CTCAE if these events are judged to be possible, unlikely or unrelated to study drug. If the drug must be held for more than three days, the participant will need to come off the study.

	Remain at 25 mg dose instead of increasing to 50 mg	Dose reduction to 25 mg dose after increasing to 50 mg dose	Dose hold at either 25 mg or 50 mg dose for up to 3 days
Conditions	
 Substantially reduced fatigue on 25 mg dose Adverse events grade II or higher determined by CTCAE guidelines Other conditions deemed significant by the research nurse and study psychiatrist 	
 New onset adverse events grade II or higher by CTCAE guidelines definitely or probably related to study drug Other conditions deemed significant by the research nurse and study psychiatrist 	
 Adverse events grade II or higher by CTCAE guidelines possibly, unlikely, or unrelated to study drug Other conditions deemed significant by the research nurse and study psychiatrist

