Naltrexone blocks the effects of opioid analgesics and should not be used in patients who are currently on opioid analgesia, who have received opioids within the past 7 days (14 days for longer-acting opioids such as methadone), or who are expected to require opioid analgesia within the next 7 days. If opioids are required, the patient should stop naltrexone and wait 3 days before initiating opioids. If necessary, reversal of opioid blockade before the 3-day time period is possible to achieve, but should be done only under medical supervision, as higher doses may be required to achieve effective analgesia creating a risk of respiratory depression. Such supervision should occur in medical settings with the provision for respiratory support. This would include a hospital emergency department or intensive care unit.

Potential study participants will be strongly cautioned about unpleasant side effects of opioid withdrawal that may occur if they are on opioids at the time study drug is initiated. In addition, medication lists in LMR will be reviewed by study staff to verify the participant’s self-report of opioid use.

Participants may use standard doses of acetaminophen, NSAIDs, or aspirin for analgesia during the study. Subjects on daily NSAIDs of >800mg ibuprofen daily (or the equivalent) will have LFTs one week after initiation of study drug. All participants will be instructed to report any symptoms of abdominal pain lasting more than a few days, white bowel movements, dark urine, or yellowing of their eyes. In the setting of these symptoms, liver function tests will be checked immediately.

Finally, if participants require opioid analgesia emergently during the course of the study, they will be taken off study. Study staff will notify the PI and QACT so that the treatment assignment (naltrexone or placebo) can be unblinded prior to initiating opioid analgesia. If the participant was assigned to naltrexone, the opioid analgesia will need to occur in a supervised medical setting, as above.

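### The stopping rules take patients off the study, not only off drug, and nothing says whether the scheduled week-5 and week-9 FACIT-F still apply

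*Combined protocol and SAP*

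**What the plan says.** Four sections end study participation, not only dosing.

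- Section 5.7 lists seven criteria and says "Participants will be removed from the study when any of the criteria listed in Section 5.7 applies". Criterion 7 is "Need to hold drug for more than 3 days, for any reason".
- Section 5.8 says "If the drug must be held for more than three days, the participant will need to come off the study". Section 12.5.1 repeats that rule.
- Section 6.1 says "if participants require opioid analgesia emergently during the course of the study, they will be taken off study".

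On removal, Section 5.7 asks for the reason, the date, a form and a talk about other care. Section 12.5.2 collects dropouts' reasons for leaving, to support post-hoc analyses against missing-data bias. The Subject Exit Form records dates and reasons and has no FACIT-F.

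The intervention calendar in Section 9 lists FACIT-F at weeks 0, 1, 5 and 9, with no instruction for a patient who stops early. Section 5.6 follows intervention-phase patients to 4 weeks after treatment. It follows those removed for unacceptable adverse events to the end of the study and further, until the event resolves or stabilises. It names no questionnaire.

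Sections 12.1 and 12.5.2 restrict the main analysis to patients who complete the protocol.

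**The concern.** Criterion 7 turns almost any lasting interruption into departure from the study. Only dose reduction and holds of up to 3 days keep a patient in. A site following this text could reasonably stop collecting FACIT-F at removal, and another site could reasonably continue.

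The reasons for stopping can depend on treatment. Section 6.1 reports that about 5% of patients in controlled alcohol-dependence trials stopped oral naltrexone for nausea, and it lists fatigue itself as a side effect (at least 4%). Stopping may therefore be related to both arm and outcome.

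The post-hoc analyses in Section 12.5.2 would then have reasons for leaving but no assured score at the outcome time. An analysis of all randomised patients would have the same gap. Scores not collected at the time cannot be recovered later.

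**Working it through.** **Plan's own figures.** Section 12 gives a difference of 3.6 points, SD 10, two-sided 0.05, power 0.80, 122 per arm, 20% drop-out and about 150 per arm randomised.

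- n per arm = 2 × (1.96 + 0.8416)² × 10² / 3.6² = 121.1, rounded up to 122. The t-test solution is 122.1. The plan's figure is reproduced.
- Drop-out: 122 / 0.80 = 152.5, or 122 × 1.20 = 146.4. Both are close to 150.
- 150 × 0.80 = 120 completers per arm, power 0.796. The sample size already allows for these patients, so the issue is possible bias and not the number of completers.

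**Patients whose scores are not assured.** 0.20 × 300 = 60.

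- If removal cancels the remaining visits, all 60 lack a week-5 score.
- If the scheduled visits stand, the removal rule costs 0 scores.
- The text does not choose between these. The 60 is an upper limit because it includes consent withdrawals and losses. The week-1 FACIT-F will usually exist, except for very early stops.

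**What the scores would let one check (illustration, assumed inputs).** Let a share p₁ (naltrexone) and p₀ (placebo) be removed, and let removed patients change g points less than completers. The completer difference then exceeds the all-randomised difference by g × (p₁ − p₀).

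- 25% against 15%, g = 5: 5 × 0.10 = 0.5 points. With g = 10: 1.0 point.
- With no true all-randomised difference, completers number 112.5 and 127.5 per arm and SE = 10 × √(1/112.5 + 1/127.5) = 1.29. Two-sided rejection is then about 6.7% (0.5 points) or 12.1% (1.0 point) instead of 5%.
- Equal removal with equal g: shift 0.

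This shift comes from the completer-only analysis set. The missing scores matter because without them nobody can see whether it occurred.

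**Power of an all-randomised sensitivity analysis (best case, all 150 per arm give data).** SE = 10 × √(2/150) = 1.155. Power = Φ(difference / SE − 1.96). With 20% stopping:

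| Effect kept by stoppers | Difference | Power |
|---|---|---|
| All | 3.60 | 0.88 |
| Half | 3.6 × (1 − 0.20 × 0.5) = 3.24 | 0.80 |
| None | 3.6 × (1 − 0.20) = 2.88 | 0.70 |

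The effect kept is an assumption. Real power would be lower, because withdrawals and losses give no data.

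**The case against.** The strongest counter-argument is Section 5.6. For adverse events, the most obvious treatment-dependent reason for stopping, it already continues follow-up to the end of the study, and resolution of the event governs only what comes after. Section 9 schedules FACIT-F at weeks 5 and 9, so a careful site might collect it. This stands in part: removal does not end all follow-up, and a reader who infers that every removed patient disappears goes beyond the text. But Section 5.6 does not connect its follow-up to FACIT-F and does not address removal for opioids, protocol deviation or other holds. Its general sentence on follow-up to 4 weeks after treatment does not mention removed patients.

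A reader might also infer that the plan sets three competing outcome times for an early stopper. Section 1.1 has one visit "one at the conclusion of medication treatment for treatment outcome assessment and safety monitoring (week 5") and another, "the last at four weeks after discontinuation of study drug vs. placebo (week 9"), while Section 5.3 times the outcome visit "five weeks after initiating study drug vs placebo". The documents do not support that reading. Section 1.1 labels its visits week 5 and week 9, and for the planned course all the texts agree. They describe scheduled visits and are not rival rules for patients who stop. Counts of missing scores between 0 and 60 would need that reading plus an assumed spread of stopping times, so none is given here.

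Finally, it can be said that collecting the scores changes nothing in the planned result, and that scores after opioid start or unblinding are hard to interpret. Both are true. They limit the weight of the point but do not remove it.

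**Conclusion.** The point holds and is worth fixing. The plan equates stopping drug with leaving the study and does not say whether the scheduled FACIT-F visits survive removal. Outcome scores are not assured for up to about 60 of 300 patients, with a range of 0 to 60 according to how the text is read. This rests on the plan's 20% drop-out and on the protocol text; the study-plan figure in Section 5.1 was not available for this check.

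It would be tempting to conclude that this rule biases the primary result. It does not do so by itself. Sections 12.1 and 12.5.2 count completers only, so collecting more scores leaves that result as it is. The loss is a check on the completer result that cannot be built after the trial.

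**What to change.** Keep every stopping rule. In Sections 5.7, 5.8, 6.1 and 12.5.1, replace removal from the study with discontinuation of study drug. Reserve off-study status for consent withdrawal, loss to follow-up or the end of follow-up. The registration office's form already separates the two states: it "should be filled out when a participant completes study treatment and again when the participant comes off study".

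In Section 5.6, state that every randomised patient gives FACIT-F at weeks 5 and 9, whatever the reason drug stopped, unless consent is withdrawn. Count the weeks from first dose, or from randomisation if no dose is taken, with the existing ± 7 days and by phone if needed (Section 5.3 already allows phone contact in the monitoring phase). A fixed date matters because Section 2.2 expects this fatigue to recover spontaneously after radiotherapy.

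In Section 12, name a sensitivity analysis of all randomised patients with FACIT-F data, and flag scores given after unblinding or opioid start.

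The cost is a wording amendment and at most 60 × 2 = 120 questionnaires of 13 items, fewer in practice. The effect in the sensitivity analysis may be diluted, with the best-case power shown above. The planned completer analysis is untouched.
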